### 2.1 Background to the proposed research

1) What clinical unmet need are you addressing with the proposed research?

To investigate whether the efficacy of the Glaucoma eye drops to reduce IOPs can be made more effective. This would reduce the burden to the patient in terms of side effects and drop frequency and reduce the cost to the NHS.

2) What novel solution / technology are you proposing to meet the clinical need identified?

The eyelids will be heated using Blephasteam® or an equivalent device, a medical device consisting of a pair of goggles designed to relieve the symptoms of Meibomian Gland Dysfunction (MGD). The eyepieces of the goggles provide latent heat without pressure and once the moistened insert is included provides a high humidity environment (Jones et al., 2017). These eyepiece chambers promote fluidisation of the secretions in the glands. The alternate current supplied wireless device will be plugged in for 3-4 minutes to reach temperature, a light indicates when it is ready for use. A water carrier will be filled with drinking water will be inserted into the mask, the goggles are worn for 10 minutes, which is timed by the device. It has been reported that moist and non-moist lid-warming devices are equally efficient at improving the symptoms of MGD (Arita, et al., 2015). In this study we are repurposing this piece of equipment to investigate whether it can enhance the effect of the eye drops and further reduce IOP when used in conjunction with hypotensive eyedrops. Each patient will have their own water carrier for hygiene purposes.

3) Are there competing solutions / technologies that are already available in the clinic or are currently being developed?

We have performed an extensive literature search in conjunction with our library service to determine whether there are currently any other studies or similar approaches being employed in a manner that we have put forward in this feasibility study. There is anecdotal evidence that the application of heat can enhance the effectiveness of mydriatric drops. There have been no studies that have tested the concept of applied eyelid heat in combination with anti-glaucoma medication in humans.

4) What is the advantage of your proposed solution compared to solutions / technologies that are already available in the clinic or are currently being developed?

The advantage of the approach proposed in this study is to utilise an existing medical device

that would be readily available to patients and can be reused. By using this device in conjunction with their hypotensive eye drops it is hoped that the effectiveness of their current treatment will be enhanced and as a secondary action may also improve any MGD which is frequently reported in patients medically managed for Glaucoma.

## **3 THEORETICAL FRAMEWORK**

There is a lack of evidence that applying heat to the eyelids may improve ocular drug delivery in all areas of Ophthalmology. This feasibility study has chosen to focus on the hypothesis that the addition of heat will enhance the efficacy of ocular hypotensive eye drops used in the treatment of POAG and OHT will result in a significant reduction in IOPs when compared to the use of ocular hypotensive eye drops alone. There is a great potential use for a favourable outcome from this study in that it could reduce the need for additional eye drops or progression to surgery. It is currently well accepted that applying heat to the eyelids is a safe procedure and is a mainstay of treatment for MGD and it is this approach that will be used in this study to determine whether ocular drug delivery can be enhanced. The clinic at Hinchingbrooke (HH) and Peterborough City Hospital (PCH) runs regular Glaucoma clinics with a large number of these patients who have an active diagnosis of POAG or OHT. Patients will be approached that currently use their eye drops in the morning as it is thought that this in combination with the heat will enhance the effect further. If proof of concept is realised through this feasibility study, then a larger scale project will be put forward to investigate whether the effect is demonstrated in all Glaucoma hypotensive eye drops and whether it is also effective if patients instil their drops in the evening. It is acknowledged that the effectiveness of the glaucoma eyedrops could be increased with heat alone and/or with the additional beneficial effects imparted on the ocular surface by virtue of improving any underlying MGD condition. As such the baseline MGD status of all patients will be recorded to determine to what level the improvement of this condition may affect the overall outcome.

## 4 RESEARCH QUESTION/AIM(S)

To investigate whether applying heat to the eyelids of patients with POAG or OHT in combination with ocular hypotensive eye drops results in further lowering of IOP.

## **Primary objective**

The primary objective of the study is to demonstrate that heat applied directly to the eyelids in combination with the instillation of anti-Glaucoma eye drops induces a further lowering of IOPs when compared to the use of anti-Glaucoma eye drops alone.

## Secondary objective

The secondary objective of the study is to determine whether there is a timepoint during the

course of the day (phasing) that demonstrates the largest difference in IOP following heat and hypotensive eye drop combination.

### 4.1 Objectives

### 4.1.1 Primary objective:

1. The mean difference of IOP in the same eye (right eye) from the baseline IOP and after the bilateral heat intervention.

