#### **STUDY FLOW CHART**

Suitable patients identified and consented from Glaucoma clinics at HH and PCH-visual fields test completed One week prior to the first phasing visit the patient will be asked to start completing their drop compliance diary, continued for the duration of the study IOP phasing for POAG/OHT patients on topical therapy WITHOUT heat (no mask) - first visit IOP phasing for POAG/OHT patients on topical therapy WITH heat - second visit IOP phasing for POAG/OHT patients on topical therapy WITHOUT heat (wearing mask) third visit One to two weeks after completing the study a further visual fields test will be completed safety visit including a visual fields test and visual acuity measure Patient continues with their normal Glaucoma care

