## 5 STUDY DESIGN and METHODS of DATA COLLECTION AND DATA ANALYIS

This is a feasibility single-centred, interventional study that will evaluate the impact of using heat applied to the eyelids in reducing IOP measured over the course of a day (phasing) in POAG and OHT patients. The trial will involve 24 patients with a diagnosis of POAG with IOPs ≤24mmHg or OHT with IOPs ≤ 30mmHg. Participants would already be using a prostaglandin analogue (PGA) eyedrop monotherapy instilled in the morning-this approach has been adopted to reduce the variability of the results. Before the baseline visit the principle

investigator (PI) or research optometrist will receive consent from the patients, who will then undergo a visual fields test (Humphrey sita fast 24-2) if one has not already been completed in the previous three months.

One week prior to the baseline visit and whilst participating in the study the patients will be asked to complete a 'drop compliance diary' documenting when and how frequently they are using their Glaucoma medication. This is to ensure that they are adhering to their advised schedule of drop regime beforehand and that taking part in the study is not influencing their habitual drop routine. This approach is to help confirm that the reason for any reduction in IOP over the course of the study can be more confidently attributed to the intervention of heat rather than a possible phenomenon that being part of the study might naturally improve compliance with their eyedrops and hence IOP would be reduced in this manner.

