### Primary analysis:

1. Mean difference of IOP will be analysed using paired t-test if normally distributed or using Wilcoxon signed rank test for pared cases if not normally distributed.

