## 7.4 Summary

POAG and OHT patients using a prostaglandin analogue monotherapy will be recruited to undergo a series of IOP phasing visits with and without heat applied to the eyelids. There will also be a 'control' phasing visit whereby the participant will wear the mask but the heat aspect will not be activated. The study will measure the change in IOP (using the Goldman and ORA tonometers) to establish whether there is any significant difference in IOP with or without the heat when combined with the patient's habitual glaucoma drop therapy, and at which time point during the day displays the maximal effect.

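### The primary contrast bypasses the unheated-mask control visit, so any effect of wearing the goggles is counted as an effect of heat

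*Protocol*

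**What the plan says.** Each participant has three phasing days in a fixed order, about a week apart (protocol, section 5). The flow chart describes the first as "IOP phasing for POAG/OHT patients on topical therapy WITHOUT heat (no mask) - first visit", the second as phasing with heat, and the third as "IOP phasing for POAG/OHT patients on topical therapy WITHOUT heat (wearing mask) third visit". Section 5 introduces the third day as a control, and section 7.4 repeats this: "There will also be a 'control' phasing visit whereby the participant will wear the mask but the heat aspect will not be activated".

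The primary objective in section 4 is to show that heat plus drops "induces a further lowering of IOPs when compared to the use of anti-Glaucoma eye drops alone". Section 4.1.1 turns this into "The mean difference of IOP in the same eye (right eye) from the baseline IOP and after the bilateral heat intervention". Section 5.2.1 tests it once: "Mean difference of IOP will be analysed using paired t-test if normally distributed", with a Wilcoxon signed rank test otherwise.

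Section 5.2.2 adds a one-way repeated-measures ANOVA for each phasing day, and paired t-tests at single time points with versus without heat. It also tabulates adverse events and safety variables by whether heat was received. It treats a difference of 1.5 mmHg as a significant change, with P below 0.05.

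**The concern.** The hypothesis in section 3 attributes the extra lowering to the addition of heat. Visit 2 differs from visit 1 by more than heat: the participant also wears the goggles, sits in a closed chamber and goes through the supervised mask routine. Visit 3 exists to separate these components from heat, and it costs each participant a full day of five IOP time points. A primary contrast that leaves it out cannot tell a heat effect from a mask effect.

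Section 4.2 says that confirming the hypothesis would lead to an expanded study with other trusts. A result wrongly credited to heat would therefore shape that study's rationale and design.

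**Working it through.** **Step 1. Which visit is baseline?** Section 4.1.1 does not define baseline IOP. Section 5 starts the drop diary thus: "One week prior to the baseline visit and whilst participating in the study". The flow chart says: "One week prior to the first phasing visit the patient will be asked to start completing their drop compliance diary". Together these equate the baseline visit with visit 1. Section 7.3 also uses the word baseline for the consent appointment, but the schedule of procedures lists no study IOP before visit 1. Visit 1 is the most plausible reading, although it is inferred.

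**Step 2. Where does visit 3 enter the analysis?**

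| Analysis | Includes visit 3? | Compares conditions? |
|---|---|---|
| Primary paired test (4.1.1, 5.2.1) | No, on the reading in step 1 | Yes |
| Per-day ANOVA (5.2.2) | Yes, as one phasing day | No, time points within a day |
| Time-point paired t-tests (5.2.2) | Unclear: visits 1 and 3 are both without heat | Yes |
| Adverse event and safety tabulation (5.2.2) | Yes, under no heat | Descriptive only |

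Visit 3 data are used in places, but no contrast between conditions specifies that visit.

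**Step 3. What each contrast estimates.** Let h be the heat effect, m the effect of wearing the mask without heat, and p1, p2, p3 the period effects of the three visits.

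- Visit 2 − visit 1 = h + m + (p2 − p1)
- Visit 2 − visit 3 = h + (p2 − p3)
- Visit 3 − visit 1 = m + (p3 − p1)

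The primary contrast carries m in full. Visit 2 − visit 3 removes m but keeps a period term, because the order never varies.

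**Step 4. Illustrative size.** The protocol supplies n = 24 (section 7.2.1) and a 0.05 threshold (section 5.2.2). It gives no sidedness, so two-sided is assumed. It gives no SD of paired differences and no mask effect, so both are assumed. No power calculation is available to reproduce: the 24 rests on pilot-study references and budget, and 2 × 12 = 24 matches the title of one cited rule of thumb.

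Set h = 0 and all period effects to 0. The paired t-test has 23 degrees of freedom and critical value 2.069. Its noncentrality is m / (SD/√24). The probability of a significant lowering is the noncentral-t tail beyond 2.069. For SD 3 and m = 0.5, the standard error is 3/√24 = 0.612, the noncentrality is 0.5/0.612 = 0.816 and the probability is 0.120. For m = 1.0 the noncentrality is 1.633 and the probability is 0.346.

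| Assumed SD of differences (mmHg) | m = 0.5 mmHg | m = 1.0 mmHg |
|---|---|---|
| 2 | 22% | 65% |
| 3 | 12% | 35% |
| 4 | 8% | 22% |

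The nominal rate in that direction is 2.5%. The assumed values of m are one third and two thirds of the protocol's 1.5 mmHg (0.5/1.5 and 1.0/1.5).

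**Step 5. Effect of the change on sample size.** Visit 2 − visit 3 is still a paired comparison in the same 24 people. The 95% CI half-width, 2.069 × SD/√24, is 0.84, 1.27 or 1.69 mmHg for SD 2, 3 or 4. This holds for either contrast if the SD is the same.

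**The case against.** The strongest reply is that the written objective compares heat plus drops with drops alone, and visit 1 is literally drops alone. Visit 2 minus visit 1 matches that wording and validly targets the total effect of the heated-goggle package. This stands: section 4.1.1 does not contradict the objective. It does not rescue a claim about heat itself, which is the hypothesis in section 3 and the reason for having an unheated-mask control.

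A reader might infer that the control visit is used in no analysis at all. The protocol does not support that. The per-day ANOVA covers visit 3, the safety tabulation places it under no heat, and the time-point tests could include it.

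A reader might also infer that visit 2 versus visit 3 isolates heat. It does not, because visit 3 always comes last. The conduct of visit 3 is also not fully pinned down. Unheated wear time is not stated separately, so ten minutes is inferred from section 5. The schedule marks Blephasteam application only at visit 2, though that table may be damaged by extraction. Sections 5 and 7.3 disagree on whether the eyes are closed or open in the mask, and they need to be reconciled.

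Finally, nothing in the protocol shows that goggle wear lowers IOP. That is correct, and the percentages above are conditional on it. Ruling such an effect out is what the control is for.

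This is a small feasibility study, and an analysis plan not shown here may define the unheated comparator. However, the protocol itself fixes the primary contrast, and a plan that followed it would inherit the problem.

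**Conclusion.** The point holds in a limited form. The primary contrast sets the heated-mask day against what is most plausibly the no-mask day. No contrast between conditions names the visit the protocol calls its control, and the unheated comparator in section 5.2.2 is undefined. Any effect of wearing the goggles enters the estimated heat effect one for one.

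How much this matters in mmHg cannot be read from the protocol. On assumed mask effects of 0.5 to 1.0 mmHg, the false-lowering rate runs from 8% to 65% across SDs of 2 to 4 mmHg. This range illustrates the risk and is not a forecast. It also assumes no period effect and no heat effect.

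**What to change.** In sections 4.1.1, 5.2.1 and 5.2.2:

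- Define baseline IOP as visit 1, and state for each test which visit the unheated comparator is.
- Specify the within-participant right-eye difference in mean phasing IOP, visit 2 minus visit 3, as the contrast on which any claim about heat rests. It can be primary, or co-reported and required for that claim.
- Report visit 2 minus visit 1 as the total effect versus drops alone, and visit 3 minus visit 1 as the mask effect.
- State that, with the fixed visit order, visit 2 minus visit 3 removes the mask component but remains confounded with period.

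The cost is a wording change. The planned visits already supply the data, and the sample size stays at 24. The small downside is that the claim about heat no longer rests on the literal drops-alone comparison in the objective, which moves to the total-effect analysis. Randomising visit order would address the period term, but it is a separate design change affecting visit conduct, the flow chart and the schedule, and this fix does not depend on it.

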### 4.1.2 Secondary objectives:

1.Adverse events

2.QoL questionnaires

### 4.2 Outcome

Should this study confirm the proposed hypothesis it would be the intention of the researchers to expand the scope of the study by collaborating with other NHS trusts to increase subject recruits, include broader patient demographics and a wider range of anti-hypotensive eye drops to investigate whether a particular class of drug would be more sensitive to temperature and whether gender or race has an effect on the IOP. Although it is not within the scope of the current budget applied for, future studies would also include a non-glaucomatous control group who would undergo the same IOP phasing protocol with and without the heated goggles to establish whether heat alone would be sufficient to reduce the IOP in comparison to the combination of heat and anti-hypotensive eye drops in Glaucoma patients. It would be the intention of this research team to apply for further funding to support this action from charities such as Glaucoma UK which encourage applications from Optometrists to the open call Glaucoma care grant.

## 5 STUDY DESIGN and METHODS of DATA COLLECTION AND DATA ANALYIS

This is a feasibility single-centred, interventional study that will evaluate the impact of using heat applied to the eyelids in reducing IOP measured over the course of a day (phasing) in POAG and OHT patients. The trial will involve 24 patients with a diagnosis of POAG with IOPs ≤24mmHg or OHT with IOPs ≤ 30mmHg. Participants would already be using a prostaglandin analogue (PGA) eyedrop monotherapy instilled in the morning-this approach has been adopted to reduce the variability of the results. Before the baseline visit the principle

investigator (PI) or research optometrist will receive consent from the patients, who will then undergo a visual fields test (Humphrey sita fast 24-2) if one has not already been completed in the previous three months.

One week prior to the baseline visit and whilst participating in the study the patients will be asked to complete a 'drop compliance diary' documenting when and how frequently they are using their Glaucoma medication. This is to ensure that they are adhering to their advised schedule of drop regime beforehand and that taking part in the study is not influencing their habitual drop routine. This approach is to help confirm that the reason for any reduction in IOP over the course of the study can be more confidently attributed to the intervention of heat rather than a possible phenomenon that being part of the study might naturally improve compliance with their eyedrops and hence IOP would be reduced in this manner.

The patient will attend the clinic for three separate visits each approximately one week apart. starting with phasing 'without heat', then phasing 'with heat' and lastly phasing wearing the Blephasteam mask but with no heat as a control. The Blephasteam mask will only be used on the days of the clinic visits, the participants will not be required to use the device at home. The water carrier inserts for the masks will be designated to the same patient throughout the study for hygiene reasons. The inserts for the mask will be moistened and fitted according to the manufacturers' instructions. The wireless device will be left to reach temperature for 3-4 minutes then the patient will be asked to wear the mask and be instructed to keep their eyes closed, this occurs once at the start of each visit. The device warms the ocular surface for a set time of 10 minutes, after which the participants will remove the mask and instil their habitual Glaucoma eyedrops. They will be instructed to close their eyes and apply light pressure on the inner corner of the eye for 30 seconds. The IOP will then be measured at the first time point with the ORA and Goldman devices. Although both eyes will be treated with the heat mask only the right eve results (to eliminate bias) will be used for the statistical analysis. During the visits the patients' will have their best corrected visual acuity (BCVA) reviewed before and after measurements are taken. IOPs are measured first using the ORA tonometer (Reichert Inc., Germany) followed by the Goldman tonometer (Haag-Streit AG, Switzerland) five minutes later as per previous studies measuring IOP with the sequential use of tonometers (Tejwani et al., 2015). These IOP measures are taken at five set time points during the day called 'phasing': 08:30 +/- 30 mins, 10:30 +/- 30 mins, 12:30 +/- 30 mins, 14:30 +/- 30 mins and 16:30 +/- 30 mins. An average of three measures will be taken using the ORA machine, when using the Goldman tonometer three measures will only be taken if the first two are not within >2mmHg of each other. The procedure for the Goldman tonometer will be as follows: Two individuals (an operator and a reader) will perform the readings for the study visits. The operator will be responsible for operating the slit lamp, tonometer, and the instrument dial, while the reader will read and record the results. A full anterior segment slitlamp examination will be performed at the end of each phasing visit to ensure there are no adverse effects experienced following the treatment, including grading of the Meibomian glands (Efron scale). Additional assessments include adverse events and quality of life and ocular questionnaires.

One to two weeks after completion of the study the patients will undergo a further visual

fields test (Humphrey sita fast 24-2) to ensure no significant progression of their disease has occurred as a result of the study regime. All data will be recorded and stored for analysis at the end of the trial and made available to the standard of care treating clinician. At the end of the trial the patients will continue their Glaucoma visit schedule as requested by their treating Ophthalmologist.

All attempts will be made to have participants complete the study by organising visits that fit in with their timetable and offering further appointments should the participant not be able to attend on a certain day. Participants will be offered reimbursement for travel and refreshments on the day of their study visits. In the case of participant 'drop-outs', the research team will attempt to recruit further participants otherwise patients on whom all the tests could not be performed will be excluded from analysis.

When designing this trial, it was important for us to ensure that the comments and suggestions of the public and patients were taken on board, so that we could confirm that this trial was suitable for people with POAG or OHT. To do this, a patient and public involvement (PPI) forum was be organised on 30th May 2023 and the trial subsequently developed with the help of people diagnosed with Glaucoma in the Cambridgeshire area who agreed that the tests and procedures included in this study were practical and acceptable to patients.

It is the intention of the research team that the results of the study will be disseminated in peer-reviewed articles and at ophthalmic conferences.

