## 5.2.2 Datasets

To determine whether there is a significant change in IOP in each participant, the IOP measured with and without the addition of heat over the five time points will be used in a one-way repeat measure ANOVA test will be completed for each day of phasing. A paired ttest will be used to establish significance between an individual's IOP measure at a certain time point with or without the addition of heat. A difference of 1.5mmHg in IOP mean deviation would be considered a significant change of IOP. This value has been used in previous Glaucoma studies (Allergan Bimatoprost SR and Thea In-Sight) to provide a 95% confidence interval. A paired t-test will be used to establish any significant change in BCVA at baseline and exit visit based on a mean SD change of 0.1 logMAR or 5 ETDRS letters. Ocular safety parameters, QoL (EQ-5D-5L) and OSDI questionnaires, visual fields and slit-lamp exam measures will be summarised for the cohort by mean, standard deviation (SD), median, minimum and maximum values. A non-parametric analysis (Wilcoxon signed rank test) will be used if the data is found to not be normally distributed. Ocular adverse events and safety variables will be tabulated by whether the participant has received heat treatment or not before instilling their anti-hypotensive eye drops. Normality of the data will be checked by plotting histograms of the data (separately before and after the heat) and not using stats tests. Differences will be considered statistically significant P values less than 0.05.

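### One fixed visit order for every participant confounds the primary baseline-versus-heat comparison with visit number, and the unheated-mask visit protects against this only in part

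*Protocol*

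**What the plan says.** Section 5 of the Protocol fixes the order of conditions: "starting with phasing 'without heat', then phasing 'with heat' and lastly phasing wearing the Blephasteam mask but with no heat as a control". The Study Flow Chart repeats it, with "IOP phasing for POAG/OHT patients on topical therapy WITHOUT heat (no mask) - first visit" followed by "IOP phasing for POAG/OHT patients on topical therapy WITH heat - second visit", and the Schedule of Procedures in the appendix has the same columns. Spacing is also in Section 5: "The patient will attend the clinic for three separate visits each approximately one week apart". No random or counterbalanced order is described anywhere.

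The primary measure in Section 4.1.1 is "The mean difference of IOP in the same eye (right eye) from the baseline IOP and after the bilateral heat intervention". Section 5.2.1 tests it simply: "Mean difference of IOP will be analysed using paired t-test if normally distributed", with the Wilcoxon signed rank test as the alternative. Section 5.2.2 adds "Differences will be considered statistically significant P values less than 0.05" and treats 1.5 mmHg as the size of a significant change. No analysis in Section 5.2 has a term for visit number or uses the diary.

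Section 5 recognises a rival explanation. It gives the purpose of the drop compliance diary as letting a fall in IOP be "more confidently attributed to the intervention of heat rather than a possible phenomenon that being part of the study might naturally improve compliance". Participants keep this diary from one week before the baseline visit.

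**The concern.** The stated purpose is to show that heat lowers IOP further than drops alone. If heat is always visit 2 and its comparator always visit 1, a change from the first visit to the second cannot be told apart from a heat effect in that comparison. Two such changes are plausible: better drop use because the participant is being studied, and a participant more at ease with tonometry. A fall from either would be reported as efficacy, and a rise would hide a real effect. Section 2 intends the result as proof of concept for a larger study, so the error would carry forward. A later analysis plan cannot repair this, because the order is set by how the visits are run.

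**Working it through.** **Which visit is baseline.** Section 4.1.1 does not define it. Section 5 starts the diary one week before the baseline visit, and the Flow Chart starts it one week before the first phasing visit, so the two coincide. Section 7.3 also uses the word for the consent appointment, but the Schedule of Procedures lists no IOP there. Visit 1 is therefore the working reading.

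**What each contrast estimates.** Let *h* be the heat effect, *m* the effect of wearing the mask, and *p2*, *p3* the visit effects relative to visit 1. The expected visit means are:

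- V1 = μ
- V2 = μ + h + m + p2
- V3 = μ + m + p3

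Therefore:

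- V2 − V1 = h + m + p2 (the primary contrast)
- V2 − V3 = h + p2 − p3
- V2 − (V1 + V3)/2 = h + m/2 + p2 − p3/2

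In the primary contrast a shift *p2* adds to *h* in full. Three means cannot identify five parameters (μ, h, m, p2, p3): the design matrix has rank 3 and *h* is not estimable. Dropping the mask effect but leaving visit effects free (rank 3 of 4) does not help. Nor does keeping the mask effect with a linear trend (rank 3 of 4). Heat becomes estimable in two cases:

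- No mask effect and linear drift (m = 0, p2 = d, p3 = 2d): the third contrast gives h + d − 2d/2 = h.
- No order effect, strictly none between visits 2 and 3 (p2 = p3): V2 − V3 gives h, provided heat does not carry over into visit 3.

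If compliance improves once and then holds (p2 = p3 = d), the primary contrast is still wrong by *d* and the third contrast by *d*/2.

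**Size.** The Protocol gives no figure to reproduce here: Section 7.2.1 takes 24 from pilot-study references and budget, without an SD or power. Inputs: n = 24 (Section 7.2.1); 0.05 (Section 5.2.2; two-sided assumed, as sidedness is not stated); no true heat or mask effect; drift *d* and SD of paired differences assumed.

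Probability of a falsely favourable result = 1 − F(2.069; 23 df, noncentrality λ), where F is the noncentral t distribution function, 2.069 is the 97.5% point of t on 23 df, and λ = d√24/SD. For d = 0.5 and SD = 3, λ = 0.5 × 4.899/3 = 0.816.

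| Drift (mmHg) | SD 2 | SD 3 | SD 4 |
|---|---|---|---|
| 0 | 2.5% | 2.5% | 2.5% |
| 0.5 | 22% | 12% | 8.5% |
| 1.0 | 65% | 35% | 22% |

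Requiring also an observed mean fall of at least 1.5 mmHg, by integrating over the sample variance:

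| Drift (mmHg) | SD 2 | SD 3 | SD 4 |
|---|---|---|---|
| 0.5 | 0.7% | 5% | 8% |
| 1.0 | 11% | 20% | 20% |

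**Under a random order.** There are 3! = 6 sequences, and 24/6 = 4 participants in each. Every condition falls at every visit number in 2 of 6 sequences, that is 8 of 24 participants. With sequence, heat, mask and categorical visit terms the design matrix has full rank (10 of 10), so *h* is estimable apart from visit number, assuming no carry-over.

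**The case against.** The strongest reply is that the design runs off, on, off. If IOP simply kept drifting down, visit 3 would lie at or below visit 2; a short-lived heat effect would show as a rebound. This stands as partial protection. A reader might infer from the fixed order that no analysis could ever separate heat from visit order, or that the diary is the only safeguard; the documents support neither. Section 7.1 requires six months of controlled monotherapy and excludes poor compliers, drops are instilled at each phasing visit, and the diary's lead-in week may absorb some compliance gain before visit 1. These make drift smaller. They do not remove it, and the stated primary contrast does not use visit 3.

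A reader might also add season and instrument drift to the list. That is weak: visits are about a week apart within a 12-month study period, and if enrolment is staggered, calendar effects need not push all participants the same way. Only effects tied to visit number are confounded as described.

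Fixed order does have one merit. The no-mask visit always precedes heat, so it cannot be contaminated by carry-over. Section 3 itself raises a possible route, through improvement of meibomian gland dysfunction. Randomising gives that protection up, so it would be wrong to call it free of new carry-over risk.

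The drift sizes and the SD are assumptions, and the 1.5 mmHg criterion, if applied as a second hurdle, lowers the error rates. Section 5.2.2 also compares IOP with and without heat, which could bring in visit 3, but it does not say so. The feasibility label carries limited weight, because the primary objective is to demonstrate an effect.

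**Conclusion.** The point holds for the primary comparison. With baseline as visit 1, heat and second visit are the same variable, and any visit-number effect biases the estimate by its full amount. This follows from the order alone and needs no assumed SD. Visit 3 offers partial protection, under the conditions shown above.

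The size is illustrative: at an assumed SD of 3 mmHg, a 0.5 or 1.0 mmHg drift raises the chance of a falsely favourable p<0.05 from 2.5% to 12% or 35%, or to about 5% or 20% if a 1.5 mmHg fall is also required. The documents do not show that such a drift will occur, so they do not support a prediction that the trial will give a false result. They support the narrower conclusion that a fall at visit 2 could not be attributed to heat from the stated primary comparison. The change is cheap enough to make before the first phasing visit.

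**What to change.** Randomise the order of the three conditions over the six sequences, four participants each, and include visit number (period) in the primary analysis. Let a replacement for a drop-out take the vacated sequence, to keep the balance. Where existing staffing allows, do not tell the tonometer reader the condition; random order alone will not conceal it, since Section 8.1 has staff help participants use the device.

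Cost: a randomisation list and a wording change, with no extra visits, participants or measurements. Visit booking and mask preparation must follow the list. Heat would precede the no-mask visit in 3 of 6 sequences (12 of 24 participants), so the Protocol should state the assumption that about one week is enough washout. It already makes that assumption for the unheated-mask visit, which at present follows heat in all 24.

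If the order stays fixed, state that the visit 1 versus visit 2 contrast is confounded with visit order. Add visit 2 versus the mean of visits 1 and 3 as a sensitivity analysis, noting that it isolates heat only if drift is linear, visits are about equally spaced and the unheated mask has no effect.
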